9.4.1.10 Product(s) to be tested and supply (where applicable)

9.4.1.10.1 Wet formulation

Product name and applicable formulation(s)	Manufacturer	Details of product (approved for use/under development), GMP guarantee, supply and availability – see details above)	QP release
Freeze-dried formulation of dmLT	[REDACTED]	GMP guarantee, contracted	[REDACTED]
Wet formulation of CFA/I, CS3, CS5, CS6 and LCTBA	[REDACTED]	GMP guarantee, contracted	[REDACTED]

9.4.1.10.2 Partially dried formulation

Product name and applicable formulation(s)	Manufacturer	Details of product (approved for use/under development), GMP guarantee, supply and availability – see details above)	QP release
Spray-dried formulation of LCTBA, dmLT mixed with buffer	[REDACTED]	GMP guarantee, contracted	[REDACTED] [REDACTED]
Wet formulation of CFA/I, CS3, CS5, CS6	[REDACTED] [REDACTED] [REDACTED]	GMP guarantee, contracted	[REDACTED] [REDACTED]

9.4.1.11 Investigational Product:

New partially dried formulation		Wet formulation	
Contents	Adult dose (mg)	Contents	Adult dose (mg)
Part 1: dry powder	[REDACTED]	Part 1: dry powder	[REDACTED]
	[REDACTED]		[REDACTED]

Total volume of ETVAX®			Total volume of ETVAX®		

NA; not applicable

*: In the wet formulation, dmLT is pipetted into the 150ml of reconstituted buffer containing the vaccine

9.4.2 Packaging, labelling and storage of IMP

9.4.2.1 Packaging

The vaccine vials for both formulations are packed in boxes of 10 vials/box.

The effervescent powder for the wet formulation is packed in boxes of 20 sachets/box.

The dmLT vials for the wet formulation are packed in cardboard boxes with 30-50 vials/box.

The spray-dried formulation of LCTBA and dmLT mixed with buffer for the partially dried formulation is packed in boxes of 10-30 sachets/box.

9.4.2.2 Labelling

All IMP will be shipped directly to the study sites or to a local distribution site, according to local requirements.

Labels will comply with applicable Good Manufacturing Practice (GMP) requirements (EudraLex *VOLUME 4, Good manufacturing practices, ANNEX 13, Manufacture of investigational medicinal, products, February 2010, section 26*).

9.4.2.3 Storage

All study medication must be stored in a safe place with limited access, at the temperature given on the labels. Temperature logs should be kept for the area where the IMP is stored at the clinic. The temperature should be noted on a daily basis (working days only unless automatic readings are available).

- Vaccine vials shall be stored at 2-8°C.
- Buffer sachets for the wet formulation shall be stored at 2-25°C.
- Buffer sachets for new partly dry formulation shall be stored at 2-8°C.
- dmLT vials shall be stored at -20±5°C.
- Reconstituted diluted (200 µg/ml) dmLT shall be stored at 2-8°C. Maximum storage time is 48 hours.

9.4.3 Doses and treatment regimens

Both vaccine formulations should be administered only by the oral route. The vaccine will be administered orally twice to each subject at a target interval of 14 days. If the subject is unable to come for the second dose at the third study visit on day 15 due to *e.g.* illness or rules regarding quarantine due to the COVID-19 epidemic, the second vaccine dose can be administered up to 28 days after the first dose. A prolonged interval between vaccine doses did not affect the serum responses to the highly homologous CTB component of the cholera vaccine Dukoral when tested in Swedish volunteers [32]. Thus, serum CTB-specific IgA and IgA responses were comparable in both magnitude and frequency in subjects receiving Dukoral 14 days or 28-48 days apart.

9.4.3.1 Preparation and administration of investigational products

To maintain blinding of the study, the investigational products will be prepared by un-blinded trained nurses on the day of vaccination (Day 1 and day 15) at the clinic.

NOTE: The vaccine will be given to the participants by a blinded study nurse.

Detailed instructions of vaccine preparation for both formulations, including dmLT reconstitution and preparation of stock dmLT will be provided in a separate IMP manual.

9.4.3.1.1 Preparation of Wet formulation

9.4.3.1.1.1 dmLT preparation

A dmLT vial is retrieved from the freezer and thawed at room temperature. 700 µl of water for injection is added to reconstitute the dmLT. After careful swirling of the ampoule 500 to 700 µl are removed from the vial to an Eppendorf tube labelled "Stock dmLT". A 1/5 dilution of this stock is done in PBS, resulting in a 200 µg/ml solution. From this preparation 50 µl (10 µg) is pipetted into the effervescent buffer vaccine preparation before administration to volunteers.

9.4.3.1.1.2 Preparation of complete Wet formulation

The vaccine supplied as a liquid, is mixed with the 150 ml of sodium bicarbonate buffer solution on the day of preparation for use on dosing day. The time of investigational product preparation will be recorded on the appropriate Accountability Record. The vaccine dose in sodium bicarbonate buffer can be stored at room temperature for up to 90 minutes prior to dosing. The buffer is used to prevent degradation of LCTBA hybrid protein, dmLT and sensitive CF antigens by the gastric acid.

Just prior to administration 10 µg of dmLT is added by pipette (50 µl). After addition of dmLT, the vaccine should be used within 30 minutes.

9.4.3.1.2 Preparation of partially dry formulation

The partially dry formulation of vaccine is prepared by adding the effervescent powder containing the dmLT and LCTBA to 150 ml of water (the time is recorded), after mixing the content of the vaccine vial is added to the mixture and the vaccine is administered to the volunteer within 30 minutes after adding the buffer powder to the water. The buffer is used to prevent degradation of LCTBA hybrid protein, dmLT and sensitive CF antigens by the gastric acid.

9.4.3.2 Vaccine oral solution

Full dose of ETVAX[®]; a tetravalent ETEC vaccine including LCTBA + 10 µg double mutant LT (dmLT) adjuvant and effervescent powder for oral solution

9.4.4 Product accountability

The IMP will be released to the study site(s) after approvals of the study protocol have been received from the IEC and the Competent Authority.

In order to maintain blinding of the study, the IMP preparation procedure will be performed by an un-blinded member of the site staff, not otherwise involved in the conduct of the study. The person who will prepare the IMP needs to be a Registered Nurse (RN). The preparation will be observed by an additional un-blinded person. Both the nurse preparing the vaccine and the observer need to sign the vaccine preparation documentation log.

The study site will maintain a Drug Dispensing Log detailing the dates and quantities of IMP received, prepared, administered/dispensed to each subject as well as study medication returned or destroyed at the end of the study. Any discrepancies between dispensed and returned products must be explained and documented. Products deliberately and/or accidentally destroyed by the Investigator or the subject must be accounted for.

All drug accountability procedures, including cold chain monitoring will be documented and will be responsible of the unblinded study staff.

The *unblinded* Monitor will verify IMP accountability and make sure that all unused IMP is adequately destroyed/returned and documented.

9.4.5 Method of assigning subjects to treatment groups

The randomization list will be generated by the [REDACTED] biostatistician and the original randomization list will be kept at [REDACTED]. Subjects will be randomized to treatment with the wet formulation or new partially dry formulation of the vaccine (1:1).

9.4.6 Blinding

This is a double-blind study and the allocation of treatments will not be disclosed until clean file has been declared and the database has been locked for primary and secondary endpoint analyses.

Hence neither the personnel directly involved in taking care of the study subjects or evaluating the results, nor the subjects themselves, will be informed which of the two different formulations of vaccine that is given. The two formulations will have identical appearance and the same smell.

However, the person who prepares the vaccines immediately before immunization and the observer will be unblinded. These persons will not be directly involved in evaluation of adverse events or laboratory results.

The unblinded [REDACTED] Monitor will visit the investigational site to review documents and records related to the preparation of the vaccine, i.e. information unblinded to treatment allocation.

[REDACTED] pharmacovigilance personnel will be un-blinded for SUSAR reporting purposes but are not involved in data analyses.

9.4.7 Emergency decoding of blinded treatment

The treatment code may only be broken by the study medical staff in case of emergency when knowledge of the treatment received is necessary for the proper medical management of the subject. The code breaking procedure should be carefully documented.

Decoding of the blinded treatment must be reported to SBH.

9.4.8 Prior and concomitant therapy

Therapies considered necessary for the subject's welfare may be given at the discretion of the Investigator.

All concomitant therapy used during and within 3 months prior to the study period must be recorded in the CRF. No other drug under investigation may be used concomitantly with the study medication.

The subjects must not participate concurrently in any other clinical study.

9.4.9 Continuation of treatment

This is a bridging study comparing two formulations of the unregistered product ETVAX[®] and thus there will be no treatment with ETVAX[®] available after end of study participation.

9.4.10 Treatment compliance

IMP will be administered at the research clinic (CTC) under medical supervision to ensure compliance.

9.5 Study assessments

The timing and frequency of study visits and assessments are presented in the schedule of events in Table 9.1 and 9.2.

Each study assessment is described in the sections below.

9.5.1 Demographics and other baseline characteristics

9.5.1.1 Informed consent

Signed informed consent must be obtained before any screening procedures are initiated. The informed consent procedure is further described in Section 5.3.

9.5.1.2 Demographic information

The following demographic data will be recorded: race, ethnic origin, gender and date of birth.

9.5.1.3 Medical/surgical history

Relevant medical/surgical history will be obtained by interview in order to verify that the eligibility criteria are met.

In addition, information regarding COVID-19 (infections and vaccinations) as well as detailed travel history to ETEC and cholera endemic countries will be collected, primarily to support evaluation of the exploratory data. This information will not be captured in the CRF, but in a separate document.

9.5.1.4 Prior and concomitant medications

Medication history (prior medications) from 3 months prior to study start until administration of the first dose of IMP will be recorded in the CRF. Prescription medications, Over-the-counter (OTC) medications, and herbal products should be asked for. Any medication used from first administration of IMP until the last follow-up assessment (concomitant medication) will be recorded.

Prior and concomitant medications will be coded according to the WHO Anatomic Therapeutic Chemical (ATC) classification system.

9.5.2 Clinical efficacy assessments

9.5.2.1 Seroconversion rates of IgA and/or IgG anti-LTB antibodies in serum.

IgA and IgG antibodies specific for LTB will be measured in serum samples collected on visit 2 and 4 using an Enzyme Linked Immunosorbent (ELISA) assay. The analyses will be performed by technical laboratory personnel at the [REDACTED], according to standardized laboratory procedures. The seroconversion rate for IgA and IgG will be determined as the frequencies of subjects having a ≥ 2 increase in LTB-specific antibody levels in post compared to pre-vaccination samples. Specifically, this will be determined by dividing the antibody titer measured in samples collected 7 days after the second vaccination (Visit 4) with the titer measured in samples collected before vaccination (Visit 2). Samples collected before and after immunization will always be analyzed on the same ELISA-plate. Fold rises in ELISA titers ≥ 2 will be considered as significant responses for both IgA and IgG.

9.5.3 Safety laboratory assessments

There will be no safety laboratory assessments performed in this study.

9.5.4 Clinical safety assessments

9.5.4.1 Physical examination

A complete physical examination will include assessments of the head, eyes, ears, nose, throat, skin, thyroid, neurological, lungs, cardiovascular, abdomen (liver and spleen), lymph nodes and extremities.

9.5.4.2 Vital signs

Systolic and diastolic blood pressure and heart rate will be measured in the supine position after 10 minutes of rest. Body temperature will be measured in the ear using a digital thermometer.

9.5.4.3 Subject Diary

The study diaries will contain questions regarding adverse events and current medication. The adverse event and medication diaries should be filled in by the subjects on the day of vaccination and five subsequent days. Information about adverse events and medication obtained from the diaries will be verified by interviewing the subject at the following clinic visit and will then be registered in the CRFs by the study nurse/physician, i.e data from study diaries will not be transcribed word by word into the eCRF.

The following solicited AEs will be included in the diary: fever, nausea, vomiting, abdominal pain and loose stools/diarrhea.

9.5.5 Exploratory assessments

All serum samples will be analyzed for LTB specific antibodies using an electrochemiluminescence (ECL) assay based on the Meso Scale Discovery platform in parallel to the ELISA IgA assay [14, 15]. The ECL results will be reported as exploratory data. Serum samples will also be analyzed for antibodies against additional antigens expressed by ETEC bacteria, such as O78 LPS, by ELISA, ECL or similar methods.

Memory cell responses will be evaluated in subsets of subjects using analysis tools recently established for assessment of responses to a number of different infections and vaccines at the

[REDACTED]. These exploratory analyses will be used to validate the new methods for analysis of long-term immunity to ETEC in order to provide additional analysis tools to be used in subsequent ETEC vaccine trials and basic research studies.

Effector T- and B-cell (plasmablast) responses will be analyzed in 40 subjects (20 immunized with the wet and 20 with the partially dry vaccine formulation). Memory T- and B-cell analysis will be performed in 20 subjects (10 immunized with the wet and 10 with the new partially dry vaccine formulation). Memory B cell responses will be assessed on day 30±7 and 75-125 after the second dose by stimulating PBMCs with substances that transform memory B cells into antibody secreting plasmablasts. The production of IgA and IgG antibodies specific for LTB and CFs will be measured in culture supernatants by ECL and/or ELISA. The antigen specificity and isotype distribution of antibodies produced by activated memory B cells will be compared to serum antibody responses at all analysis time points after the second vaccination (day 5±1, 6-10, 30±7 and 75-125) and to antibodies secreted by plasmablasts induced to circulate shortly after the second immunization (day 5±1).

Effector and memory T cell responses will be assessed by flow cytometric analysis of activation markers on T helper cell subsets before and after stimulation of cells with LTB and CFs. The production of cytokines characteristic for different T cell subsets will be evaluated by flow cytometry, ELISA, ECL or other highly sensitive immunoassays. T cell responses will be compared in samples collected before vaccination and after the second dose (day 5±1, 6-10, 30±7 and 75-125). The relation between different types of effector T cell responses and induction of early plasmablast and serum antibody responses (day 5±1 and 6-10) and memory B and T cell responses (day 30±7 and 75-125) will be analyzed.

To check the general immune status of the volunteers and their ability to form long lived memory cells in relation to the ETEC specific immune responses measured after vaccination, immune responses to other common infections and vaccinations will be measured, such as cytomegalovirus, measles, SARS-CoV-2 and tetanus toxoid. Responses will be measured in samples from both the main study and the explorative study with techniques similar to those used to analyze ETEC specific immune responses, such as ELISA, electrochemiluminescence and flow cytometry.

9.5.6 Adverse events

9.5.6.1 Definitions

Adverse Event (AE)

An AE is any untoward medical occurrence in a clinical study subject administered a pharmaceutical product and which does not necessarily have a causal relationship with this treatment. An AE can therefore be any unfavourable and unintended sign (including clinically significant abnormal values from relevant tests, such as ECGs, vital signs), symptom, or disease temporally associated with the use of an IMP, regardless of whether it is considered related to the IMP.

A *baseline event* is any medical event in a clinical study subject that occurs after signing the ICF up until the (first) administration of IMP.

Clarifications:

Diagnostic and therapeutic non-invasive and invasive procedures, such as surgery, should not be reported as AEs. However, the medical condition for which the procedure was performed should be reported if it meets the definition of an AE. For example, an acute appendicitis that begins during the AE reporting period should be reported as “acute appendicitis” and the resulting appendectomy noticed under *Comments*. Pre-study conditions, which led to elective surgery during the time of the study, are not to be reported as AEs.

If an abnormal vital sign is associated with corresponding clinical signs and symptoms, the sign/symptom should be reported as the AE and the associated laboratory result or vital sign should be considered additional information that is to be collected in the e-CRF.

Serious Adverse Event (SAE)

An SAE is any AE that:

- results in death
- is life-threatening (this refers to an event in which the subject was at risk of death at the time of the event; it does not refer to an event that hypothetically might have caused death had it been more severe)
- requires inpatient hospitalisation or prolongation of existing hospitalisation
- results in persistent or significant disability/incapacity
- is a congenital anomaly/birth defect
- is medically important (this refers to an event that may not be immediately life-threatening or result in death or hospitalisation, but may jeopardise the subject or may require intervention to prevent any of the SAEs defined above)

Examples of medically important events are intensive treatment in an emergency room for allergic bronchospasm or blood dyscrasias, convulsions that do not result in hospitalisation, development of drug dependency and drug abuse.

Planned hospitalisations or surgical interventions for a condition that existed before the subject signed the ICF and that did not change in intensity are not SAEs.

If there is any doubt as to whether an AE meets the definition of an SAE, a conservative viewpoint must be taken, and the AE must be reported as an SAE.

Serious Adverse Reaction (SAR)

The term SAR is to be used whenever either the Investigator or SBH or designee assessed the SAE as possibly or probably related to the IMP.

Suspected Unexpected Serious Adverse Reaction (SUSAR)

A SUSAR is any SAR whose nature or intensity is not consistent with the current version of the Investigator's Brochure (IB).

9.5.6.2 Assessment of severity/intensity

The Investigator must assess the *severity/intensity* of an AE using the following definitions, and record it on the *Adverse Event Form* in the CRF:

Mild	The AE does not interfere in a significant manner with the subject's normal functioning level. It may be an annoyance.
Moderate	The AE produces some impairment of function but not hazardous to health. It is uncomfortable and/or an embarrassment.
Severe	The AE produces significant impairment of functioning or incapacitation and/or it is a hazard to the subject.

If an AE changes in severity, the most severe intensity should be recorded for that AE; i.e. the AE should not be recorded twice in the eCRF.

For severity grading of AEs, please also see Appendix 3, Clinical Toxicity Grading.

9.5.6.3 Assessment of causal relationship

The Investigator must assess the *causal relationship* between an AE and the IMP using the definitions below and record it on the *Adverse Event Form* in the CRF as well as on the *Serious Adverse Event Report Form*, if applicable:

Probably	– Probably related – the AE has a strong temporal relationship to the IMP or recurs on re-challenge, and another aetiology is unlikely or significantly less likely.
Possibly	– Possibly related – the AE has a suggestive temporal relationship to the IMP, and an alternative aetiology is equally or less likely.
Unlikely	– Unlikely related – the AE has no temporal relationship to the IMP or is due to underlying/concurrent illness or effect of another drug (that is, a causal relationship between the IMP and the AE is unlikely).

An AE is considered causally related to the use of the IMP when the causality assessment is *probably* or *possibly*.

For a baseline event, a causality assessment is not relevant.

9.5.6.4 Assessment of Outcome

The Investigator must assess the *outcome* of an AE using the definitions below and record it on the *Adverse Event Form* in the CRF:

- *Unknown* - not known, not observed, not recorded, or refused
- *Recovering/resolving* - indicates that the event is improving.
- *Recovered/resolved with sequelae* - the subject recuperated but retained pathological conditions resulting from the prior disease or injury.
- *Recovered/resolved* - indicates that the event has improved or recuperated.
- *Not recovered/not resolved* - indicates that the event has not improved or recuperated.
- *Fatal* - the termination of life as a result of an AE.

9.5.6.5 Collecting and recording of AEs

AEs and baseline events identified using any of the following methods will be recorded:

- AEs spontaneously reported by the subject
- AEs observed by the Investigator or medical personnel
- AEs elicited based on non-leading questions from the Investigator or medical personnel
- AEs obtained from Subject Diaries, as described in section 9.5.4.3

Collection of baseline events starts after the subject signs the ICF and continues until the first intervention with the IMP.

AE collection starts with the first intervention with the IMP and continues until the last follow-up assessment. Any AE with start date on the day of first IMP intervention must be recorded with start time.

At the Follow-up Visit, information on new AEs or SAEs, if any, and stop dates for AEs recorded and on-going during the dosing period must be recorded.

All AEs, serious and non-serious, should be recorded in the CRFs. Reporting of SAEs

No distinction should be made between the investigational product and the reference product regarding reporting of SAEs as long as the code is not broken.

Starting from administration of first dose of IMP, all SAEs must be reported by the Investigator to [REDACTED] Pharmacovigilance, the Monitor and SBH within 24 hours of knowledge of the event, regardless of the time that may have elapsed from the time the event occurred to when the Investigator first learns of it.

All SAEs should be reported to [REDACTED] Pharmacovigilance:

E-mail: [contact]

The Initial Report should contain as a minimum the following information:

- Subject identification
- Treatment specification (to be expressed in a blinded fashion, e.g. “Treatment A/Treatment B”)
- AE diagnosis
- Time specification for the medical event
- Name of the original reporter
- Seriousness classification

A Serious Adverse Event Report Form must also be completed, signed by the Investigator and submitted to [REDACTED] Pharmacovigilance, the Monitor and Sponsor no later than three calendar days after the initial information was received. Apart from the information above, this Follow-up Report should also contain the following information:

- assessment of severity
- assessment of causality

Only SAEs that are both unexpected and related to the investigational product(s), Suspected Unexpected Serious Adverse Reactions (SUSARs), are subject to expedited reporting. SBH are responsible for informing all Investigators concerned of relevant information about SUSARs that could adversely affect the safety of subjects.

Further details are provided in a separate Safety Management Plan.

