8.2.1 Secondary endpoints

Occurrence of solicited symptoms for six days after each vaccination (day of vaccination and five subsequent days).

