9 INVESTIGATIONAL PLAN

This is a prospective double-blind, randomized, parallel-group study with the aim to demonstrate non-inferiority, in terms of immunogenicity, between the wet formulation and a newly developed partially dried formulation of selected components of ETVAX[®].

The study will be conducted at one site; CTC in Gothenburg, Sweden.

A total of 280 healthy volunteers is planned to be randomized into the study. Assuming a 10% drop-out rate, we expect 252 healthy volunteers to complete the study.

Overall description of study design

Consenting subjects will be screened for eligibility, according to study-specific inclusion/exclusion criteria within 30 days prior to the first administration of IMP (Visit 1; Screening visit). Eligible subjects will be randomized on Day 1 (Visit 2) to receive either of the two oral formulations of ETVAX[®] (1:1) and consecutively included the study.

Screening visit and Day 1 (Visit 2) may be performed on the same day, provided that the Study protocol is adhered to in all aspects, including but not limited to the Subject Information and Consent procedures outlined in section 5.3.

The treatment allocation (Wet formulation/Partially dried formulation) will be double-blinded, *i.e.* it will not be disclosed to the subjects, site staff, laboratory staff or Sponsor.

Study subjects will receive two oral doses, two weeks apart (Day 1/Visit 2 and Day 15 /Visit 3). Preferably, subjects should receive their second dose on Day 15 (± 2). However, if a subject is unable to come for the visit on day 15 ± 2 due to *e.g.* illness or rules regarding quarantine due to the COVID-19 epidemic, the second vaccine dose can be administered up to 28 days after the first dose.

Dosing will occur at the clinic. After each dose, subjects will remain at the clinic for observation for 15 min before leaving.

At each dosing visit (Day 1 and Day 15) subjects will receive adverse event and medication diaries to be completed for six days after each vaccination (*i.e.* day of vaccination and five subsequent days).

A follow-up visit will be performed 7 days (acceptable range: 6-10 days) after the last (second) dose in all study subjects (Visit 4).

Blood samples will be collected on visit 2 and 4.

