9.7.2.2 Adverse Events (AEs)

AEs and SAEs will be recorded from the start of IMP administration until the Follow-up Visit. AEs that occur before first treatment with IMP will be reported separately as baseline event.

All AEs will be described in terms of the treatment/dose at which they occurred. AEs will be coded using the Medical Dictionary for Regulatory Activities (MedDRA) and summarized by Preferred Term (PT) and System Organ Class (SOC). The number of subjects reporting AEs, and the number of AEs reported will be presented by dose group. The events will be tabulated by SOC, PT and by severity and relationship to IMP. SAEs will also be presented in separate tabulations. The number of subjects experiencing an AE in connection to each treatment will be presented.

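### For non-serious AEs a start time is required only on the first dosing day, so a symptom that begins on the Dose 2 day before dosing can be counted as a Dose 2 symptom

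*Combined protocol and SAP*

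**What the plan says.** Section 9.5.6.5 sets one explicit start-time rule for AEs in general: "Any AE with start date on the day of first IMP intervention must be recorded with start time". It serves the boundary set out just before it: "Collection of baseline events starts after the subject signs the ICF and continues until the first intervention with the IMP". Section 9.7.2.2 then has events before first treatment reported separately as baseline events.

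Subjects are dosed twice, at Visit 2 and Visit 3, and Table 9.1 shows AE reporting at both visits. Two parts of the plan use AE timing relative to each dose:

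- Section 8.2.1, the only secondary endpoint: "Occurrence of solicited symptoms for six days after each vaccination (day of vaccination and five subsequent days". The window runs by calendar day and includes all of the dosing day.
- Section 9.7.2.2: "All AEs will be described in terms of the treatment/dose at which they occurred", and "The number of subjects experiencing an AE in connection to each treatment will be presented". No rule says how an event is assigned to a dose.

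For serious events, the initial report must contain a "Time specification for the medical event", whichever dose came before. For the diary, section 9 states: "At each dosing visit (Day 1 and Day 15) subjects will receive adverse event and medication diaries". Section 9.5.4.3 adds: "Information about adverse events and medication obtained from the diaries will be verified by interviewing the subject at the following clinic visit". Neither section asks for an hour of onset.

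**The concern.** The Dose 2 day has its own before/after boundary. AE collection is already open when the subject arrives at Visit 3, and the second dose is given at that visit. Nausea or loose stools that began earlier that day, recorded by date only, need not be distinguishable in the data from a reaction to Dose 2.

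At stake is the accuracy of the Dose 2 symptom counts. They would include some background events that the Dose 1 counts leave out, because on the Dose 1 day the required start time separates them. Solicited symptoms and AEs carry most of the safety objective here: section 9.5.3 plans no safety laboratory tests and section 9.1.3 no safety committee. A time that was never collected cannot be recovered at the analysis stage.

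**Working it through.** The plan gives no figure on this point to reproduce. The check is a comparison of sections, followed by an illustration of size.

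**1. The same event on each dosing day.** Take a non-serious solicited symptom that starts in the morning before dosing.

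| | Dose 1 day (Visit 2) | Dose 2 day (Visit 3) |
|---|---|---|
| Start time required? | Yes (9.5.6.5) | No |
| Classification | Baseline event, reported separately (9.5.6.5, 9.7.2.2) | AE |
| Solicited window (8.2.1) | Recognisable as pre-dose | Falls on the first of the six Dose 2 days |
| By-dose AE presentation (9.7.2.2) | Not an AE | No attribution rule; may be shown with Dose 2 |

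**2. Could another step supply the time?** At Visit 3 AEs are asked about, the first diary is collected, temperature is taken and eligibility is checked again (Tables 9.1 and 9.2; sections 9.3.4 and 9.3.5). Any of these may bring an event to light before dosing. None requires an onset time or a before/after-dose mark. Entries in the second diary are verified at the next clinic visit, which in the main study is 6 to 10 days after Dose 2.

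**3. Where does a pre-dose event on the Dose 2 day belong?** The Dose 1 solicited window covers Days 1 to 6. Dose 2 is due on Day 15, so that window closed 15 − 6 = 9 days earlier, or 13 − 6 = 7 days earlier at the earliest permitted visit. The event lies outside the Dose 1 window and precedes Dose 2, so it belongs to neither.

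**4. Share of the window before dosing.** The window is 6 × 24 = 144 hours. For dosing at clock hour h (assumed; the documents give no dosing hour) the share is h/144:

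- 08:00: 8/144 = 5.6%
- 12:00: 12/144 = 8.3%
- 16:00: 16/144 = 11.1%

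**5. Subjects affected.** Let p be the probability per day that an unrelated symptom begins, spread evenly over 24 hours. The documents give no such rate, so 0.5% to 5% is assumed. With n = 140 per arm, all given Dose 2, the expected number of pre-dose onsets is n × p × h/24:

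- Low: 140 × 0.005 × 8/24 = 0.23
- High: 140 × 0.05 × 16/24 = 4.67

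This is about 0.2 to 4.7 subjects per arm, before allowing for subjects whose dose is deferred because they are ill.

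**6. Effect on the comparison of arms.** Let b = p × h/24 be the added background probability, from 0.005 × 8/24 = 0.17% to 0.05 × 16/24 = 3.3%. If it is independent of vaccine reactions and equal in both arms, an arm's true risk q becomes 1 − (1 − q)(1 − b). The difference between arms becomes (q₁ − q₂)(1 − b), so it shrinks by at most about 3% of its value and cannot change sign.

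**The case against.** The strongest reply is that the start-time rule has a different job. It separates baseline events from AEs, a boundary that exists only at the first dose; at Visit 3 every event is an AE whatever its hour. That explains the asymmetry, but it does not meet the need of the by-dose endpoint in section 8.2.1.

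Other replies stand in part, and they rule out stronger readings that a reader might infer:

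- **That pre-dose and post-dose events cannot be told apart.** The protocol sets a minimum and does not bar recording a time. Serious events already carry one. The Visit 3 enquiry and eligibility re-check would catch some events, and morning nausea or loose stools is among the likelier ones to surface. Section 9 also allows Dose 2 to be delayed for illness.
- **That a planned Dose 1 versus Dose 2 comparison is biased.** No such test is planned. Section 9.7.2.2 also speaks of dose groups, while section 9.1.1 has a single dose level, so some of that wording may mean the formulation arm.
- **That 5.6% to 11.1% of Dose 2 events are misassigned.** Those figures are shares of clock time under assumed dosing hours.
- **That such events should stay with Dose 1.** For the solicited endpoint this conflicts with section 8.2.1, because the Dose 1 window has already closed.

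It is also fair to say that section 9.7 defers analysis detail to the SAP and section 9.8 defers data handling to a data management plan. No text from either on this point is in the supplied document, so the e-CRF may already collect times. An attribution rule in the SAP alone would still depend on the time having been collected.

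**Conclusion.** The point holds in a limited form. For non-serious AEs the protocol requires an onset time on the first dosing day only. Under the calendar-day window, a solicited symptom that starts on the Dose 2 day before dosing and is recorded by date counts as a Dose 2 symptom. For other AEs, assignment to Dose 2 is possible rather than certain, because no rule is stated.

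The size is small: roughly 0.2 to 4.7 subjects per arm, resting on assumed dosing hours of 08:00 to 16:00, an assumed daily onset of 0.5% to 5%, even spread over the day, and no allowance for events caught at Visit 3. The recording rule is the same in both blinded arms, the endpoint is descriptive, and the primary seroconversion analysis is untouched. Priority: minor.

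**What to change.** - **Section 9.5.6.5:** extend the start-time requirement to AEs beginning on the day of either IMP administration (Visit 2 or Visit 3), or add a before/after-dose flag for those days.
- **Dosing record:** require the time of administration at both visits. Section 9.4.3.1 has preparation times recorded and section 9.4.4 asks for dates and quantities; neither states the time the dose is taken.
- **Sections 8.2.1 and 9.7.2.2, and the SAP:** count a symptom starting on the Dose 2 day in the Dose 2 solicited window only if its onset is after dosing. A pre-dose onset on that day goes in neither six-day window. In the by-dose AE tables, show it as occurring after Dose 1 and before Dose 2.

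Section 9.5.6.2 keeps one record per AE at its worst intensity, so a symptom that begins before Dose 2 and worsens afterwards would drop out of the Dose 2 window under this rule. Listing such cases separately would keep them visible.

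The cost is a few sentences, a dosing-time entry at each dosing visit, and one extra field to complete for the few events that start on the Dose 2 day.
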